8.1 Dose Levels (Based on Adverse Events in Tables below)

Dose Level	Dose	Drug Name
0	50 mg orally bid	midostaurin

8.2 Midostaurin dose adjustments for AE at least possibly related to treatment

→ → Use the NCI Common Terminology Criteria for Adverse Events (CTCAE) version 4.0 unless otherwise specified ← ←			
CTCAE System/Organ/Class (SOC)	ADVERSE EVENT	AGENT	ACTION
AT TIME OF NEXT DOSE (All treatment days of each cycle)			
Blood and lymphatic system disorders	Grade 4 Febrile Neutropenia	Midostaurin ¹	
1st event: First event days 2-28, omit midostaurin dose until recovery then restart at 50mg b.i.d
 
2nd event: Omit midostaurin until recovery then restart at 25mg b.i.d for 2 weeks and then re-escalate to 50mg b.i.d as tolerated.
 
3rd event: Third event, patient should be discontinued if neutropenia is attributable to midostaurin

			
If alternate causes of liver dysfunction have been managed, but liver dysfunction persists, Omit midostaurin until recovery to Grade 2 then restart.
 
If this is felt to be related to study drug and the re-challenge results in a subsequent Grade 3 or 4 elevation, then patient should be discontinued from treatment.

Investigations	Grade 3 or 4 increased Bilirubin, AST, or ALT		
Gastrointestinal Disorders	Grade 2 Nausea or Vomiting	Midostaurin ¹	If this develops despite use of standard anti-emetic therapy and persists for at least 3 days, Omit midostaurin for 3 days (6 doses) and resume midostaurin as tolerated.
	Grade 3 or 4 Nausea or Vomiting		If this develops and persists despite use of standard anti-emetic therapy, omit midostaurin until recovery to Grade 2 (or at least 3 days) then restart. If this is felt to be related to study drug and the re-challenge results in a subsequent Grade 3 or 4 toxicity then the patient should be discontinued from treatment.

→ → Use the NCI Common Terminology Criteria for Adverse Events (CTCAE) version 4.0 unless otherwise specified ← ←			
CTCAE System/Organ/Class (SOC)	ADVERSE EVENT	AGENT	ACTION
Gastrointestinal Disorders	Grade 3 or 4 Diarrhea		If this develops and persists despite use of standard anti-diarrheal therapy(see section 9.4), omit midostaurin until recovery to Grade 2 (or at least 3 days) then restart.
Respiratory, thoracic and mediastinal disorders	Grade 3 or 4 Pneumonitis		Omit midostaurin until recovery to ≤ Grade 1 and then resume dosing.
Investigations	Currently the effect of midostaurin on QTc interval prolongation is not fully characterized. Therefore, all patients experiencing a post baseline prolonged QTc interval must have potassium and magnesium checked and any electrolytes imbalances corrected. Additionally, the investigator should consider the risk benefit of any concomitant medications that may prolong the QTc interval. For the purpose of this trial, the correction formula according to Fredericia, i.e. QTcF is being referred to - wherever QTc is mentioned.		
	Electrocardiogram QT corrected interval prolonged- ECG > 450msec	Midostaurin ¹	If the ECG shows a QTc interval greater than 450 msec during the trial, triplicates should be performed, one minute apart to confirm the finding (after replacement of any electrolyte imbalance).
	ECG QTc interval > 450 msec and ≤ 470 msec		Check magnesium and potassium levels and correct any abnormalities. If possible, stop any medications that may prolong the QTc interval. Continue midostaurin at the same dose.
	ECG QTc interval > 470 msec and ≤ 500 msec,		Check magnesium and potassium levels and correct any abnormalities. If possible, stop any medications that may prolong the QTc interval. Decrease midostaurin to 25 mg twice daily 1 dose level for the remainder of the cycle Resume midostaurin at the initial dose in the next cycle provided that QTc interval improves to ≤ 470 msec.

→ → Use the NCI Common Terminology Criteria for Adverse Events (CTCAE) version 4.0 unless otherwise specified ← ←			
CTCAE System/Organ/Class (SOC)	ADVERSE EVENT	AGENT	ACTION
	ECG QTc interval > 500 msec	Midostaurin	Check magnesium and potassium levels and correct any abnormalities. Omit midostaurin for the remainder of the cycle, and, if possible, stop any medications that may prolong the QTc interval. If QTc improves to \leq 470 msec just prior to the next cycle, resume midostaurin at the initial dose. If QTc interval is not improved in time to start the next cycle do not administer midostaurin during that cycle.
Other Non-hematological	Grade 4 Non-Hematologic		Discontinue midostaurin for non-hematologic grade 4 toxicity (including grade 4 vomiting, diarrhea, and pneumonitis). Midostaurin should be held for other non-hematologic grade 3 toxicity until recovery to \leq Grade 2. Upon recovery, the patient may restart dosing. If additional toxicity recurs, the midostaurin dose will be reduced to 25mg b.i.d. In the event of additional toxicity requiring dose modification, further dose reductions to midostaurin 25mg Q.D. will be allowed. If the patient tolerates the lower dose of midostaurin (25 mg b.i.d), a dose increase back to 50mg b.i.d may be attempted as tolerated. Fatigue and hair loss are exempted.

¹If decitabine is held, then midostaurin will be held. If decitabine is administered, midostaurin cannot be held, but can be omitted.

All dose modifications should be based on the worst preceding toxicity. Common Toxicity Criteria for Adverse Events (CTCAE Version 4.0)

If midostaurin is omitted due to QTc prolongation or when there's any dose change, an ECG must be obtained at 7 days afterwards.

- 8.3 Decitabine dose modification:
- Modification will be done as per standard recommendation and treating physician judgement for patient's best interest and will be mainly based on non-hematological AEs.
 - For creatinine AEs, creatinine clearance will be calculated using Cockcroft formula with total body weight and gender adjustment.

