4.0 Test Schedule

All routine assessments must be performed within ± 7 days of the day indicated on the Visit Schedule.

Tests and procedures	Pre-Treatment	Active Treatment					
	≤ 7 days prior to registration*	Cycle 1, Day 1	Cycle 1, Day 8	Cycle 1 Day 21	Cycles 2 and above, Day 1	Cycles 2 and above, Day 8 ⁷	Early Discontinuation or End of Treatment
History and exam, weight, vitals, PS	X	X			X	X	X
Height	X						
Adverse event assessment	X	X			X		X
BM testing ²	X				X ²		X
Biomarkers FLT3 Mutation by PCR	X						X
Pregnancy Test	X						
Hematology group(CBC) Hgb, , PLT, WBC with diff. ¹	X	X ¹	X	X	X ¹	X	X
Serum Chemistry (magnesium, potassium, phosphorus, total bilirubin, direct bilirubin ⁵ , alkaline phosphatase, AST, ALT, creatinine)	X	X	X	X	X	X	X
Serum Chemistry (Serum Amylase & Lipase)	X	X			X		X
MUGA/Echo	X						
LDH	X						
Urine analysis (proteinuria, hematuria) ^R	X						
ECG (QTcF results preferred) ^{R 3}	X		X			X ³	X
Patient Medication Diary (Appendix III ⁴)			X		X	X	
Research Correlatives ^{R, 6}	X		X		X ⁶		

* Labs done on the same day of consent but prior to consenting do not need to be repeated.

1. CBC will be done weekly for cycle 1-4. After cycle 4, to be performed Day 1 and Day 8.
2. Bone marrow (BM) sampling will be done upon screening, and day 1 of cycle 3, 5, 9 and then as clinically needed. Recent bone marrow within 21 days (even prior to consenting) will be acceptable and FLT3 PCR could be done on peripheral blood if blasts >10%. Outside FLT3

testing at bone marrow biopsy will be allowed and used if done.

3. ECGs will be performed locally at screening, Day 8 (prior to dosing) of each cycle, and when there's any dose change due to QTc prolongation or re-initiation after a dose interruption. When a dose change occurs due to QTc prolongation or upon re-starting midostaurin, an ECG must be obtained at 7 days afterwards. QTcF results are preferred, however all reporting methods will be accepted.
 4. The diary must begin the day the patient starts taking midostaurin and must be completed per protocol and returned to the treating institution OR compliance must be documented in the medical record by any member of the care team. Patients will be asked to return all unused medication at each visit.
 5. Get direct bilirubin if total bilirubin > upper normal limit.
 6. Correlatives for blood and bone marrow. See section 14.

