9.0 Ancillary Treatment/Supportive Care

- 9.1 Antiemetics may be used at the discretion of the attending physician.
- 9.2 Blood products and growth factors should be utilized as clinically warranted and following institutional policies and recommendations.
- 9.3 Patients should receive full supportive care while on this study. This includes blood product support, antibiotic treatment, and treatment of other newly diagnosed or concurrent medical conditions. All blood products and concomitant medications such as antidiarrheals, analgesics, and/or antiemetics received from the first day of study treatment administration until 30 days after the final dose will be recorded in the medical records.
- 9.4 **Antifungal antibiotics:** It is highly recommended to avoid concomitant strong CYP3A4 inhibitors (e.g., ketoconazole, itraconazole, voriconazole, posaconazole). The suggested antifungal regimens from a drug metabolism perspective to avoid to use is described below:
Prophylaxis:
Fluconazole (moderate CYP3A4 inhibitor)
Caspofungin

If a patient requires active treatment for a fungal or mold infection and there are no other treatment options it becomes necessary to administer an azole which is a strong CYP3A4 inhibitor. If this is needed, the suggested agents from a drug metabolism and safety perspective include:

Treatment

Voriconazole

Posaconazole

These are both strong CYP3A4 inhibitors and will likely increase midostaurin concentrations, therefore, if there are no other treatment options to treat the infection, a dose reduction by 50% of midostaurin is required to compensate for the drug interactions with these strong CYP3A4 inhibitors. With intra-patient variability with regard to CYP3A4 inhibition and midostaurin pharmacokinetics, the suggested approach is to avoid strong CYP3A4 inhibitors unless there are no treatment alternatives.

- 9.5 Hydroxyurea: Can be used for control of elevated WBC/blasts at any time of treatment for patient best care and avoid complications of hyperleukocytosis.

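### The dose step for QTc above 470 and up to 500 msec does not work for a patient already below 50 mg bid for another reason

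*Combined protocol and SAP*

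**What the plan says.** Section 8.1 has one dose level, level 0, "50 mg orally bid". In section 8.2, the row for QTc above 470 and up to 500 msec directs: "Decrease midostaurin to 25 mg twice daily 1 dose level for the remainder of the cycle". The initial dose is resumed in the next cycle if QTc has come down to 470 msec or less.

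Other rules take patients below 50 mg bid:

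- After a second grade 4 febrile neutropenia (8.2): "restart at 25mg b.i.d for 2 weeks and then re-escalate to 50mg b.i.d as tolerated".
- After recurrent non-hematologic toxicity (8.2), the dose falls to 25 mg bid. If more toxicity follows, "further dose reductions to midostaurin 25mg Q.D. will be allowed".
- When voriconazole or posaconazole cannot be avoided (9.4): "a dose reduction by 50% of midostaurin is required to compensate for the drug interactions with these strong CYP3A4 inhibitors".

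On monitoring, the text under the 8.2 table requires an ECG a week after an omission for QTc, and for "any dose change, an ECG must be obtained at 7 days afterwards". Section 4.0, footnote 3, sets the routine times: "ECGs will be performed locally at screening, Day 8 (prior to dosing) of each cycle". It adds: "When a dose change occurs due to QTc prolongation or upon re-starting midostaurin, an ECG must be obtained at 7 days afterwards". Footnote 7 moves the Day 8 tests of cycle 2 onward to Day 1 when midostaurin starts on Day 1.

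**The concern.** The row gives an end dose, not a step from the dose the patient is taking. It also calls that end dose one dose level, although 8.1 names no level below the starting dose. Target and step agree only at 50 mg bid.

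A patient already reduced for another reason can have a confirmed QTc of, say, 480 msec and, by the stated target, receive no dose reduction. Because the repeat ECG depends on a dose change, an omission or a restart, that patient also gets no dated repeat. Physicians could stay at 25 mg bid, go to 25 mg once daily or omit, all under the same text.

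The azole patient shows why this matters. That patient is at 25 mg bid because midostaurin exposure is expected to be raised, and Appendix Ib lists voriconazole among drugs with possible or conditional torsades risk. Section 8.2 itself says the QTc effect is not fully characterized. Section 1.2 notes that the thorough QTc study could not examine the long-acting metabolite at steady state.

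**Working it through.** The plan gives no figure to reproduce. The check compares the row's target with each dose the plan allows, then follows the ECG rule.

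**Inputs (total daily dose)**

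- 50 mg bid: 2 × 50 = 100 mg/day (8.1).
- 25 mg bid: 2 × 25 = 50 mg/day (8.2 febrile neutropenia and non-hematologic rows). The 9.4 cut from the starting dose gives the same: 100 × 0.5 = 50.
- 25 mg once daily: 25 mg/day (8.2 non-hematologic row). The 9.4 cut applied to 25 mg bid gives the same: 50 × 0.5 = 25.
- Target of the QTc row: 25 mg bid = 50 mg/day.

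**Step 1. Stated target.** Change = (target − current) / current.

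| Current dose | mg/day | Calculation | Result |
|---|---|---|---|
| 50 mg bid | 100 | (50 − 100)/100 | −50% |
| 25 mg bid | 50 | (50 − 50)/50 | 0% |
| 25 mg once daily | 25 | 50 > 25 | not a decrease |

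**Step 2. One-step reading.** At 50 mg bid, one step down is 25 mg bid, −50%, the same as the target. At 25 mg bid, one step down to 25 mg once daily is (25 − 50)/50 = −50%, against 0% under the target. At 25 mg once daily the plan names nothing lower, and with 25 mg capsules (15.12) one a day is the smallest daily dose.

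**Step 3. Repeat ECG.** At 50 mg bid the row changes the dose, so an ECG is due 7 days later: Day 8 + 7 = Day 15, or Day 1 + 7 = Day 8 on the continuous schedule. At 25 mg bid under the stated target there is no dose change, QTc omission or restart, so neither 8.2 nor 4.0 triggers one.

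**Step 4. Wait for the next scheduled ECG.**

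- Days 8-21 schedule: Day 8 to Day 28 + 8 = 36, and 36 − 8 = 28 days. Dosing days are 8 to 21, that is 21 − 8 + 1 = 14. The other 28 − 14 = 14 days are off midostaurin, and the Day 36 ECG comes before dosing.
- Days 1-28 schedule (optional from cycle 3, section 7.11): Day 1 to Day 29, and 29 − 1 = 28 days, all of them dosing days.

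These are nominal times, since 4.0 allows ±7 days. Another dose change or restart brings an ECG sooner; re-escalation after the 2-week febrile-neutropenia step is one example.

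**The case against.** Much of the case against stands. The row is clear for a first event at 50 mg bid. Its other actions apply at any dose: triplicate ECGs, correction of potassium and magnesium, and stopping QT-prolonging drugs where possible. The routes are narrow: a second grade 4 febrile neutropenia with a 2-week reduction, an azole only when nothing else will do, or repeated non-hematologic toxicity. Each must coincide with a QTc in this band, in a trial of at most 26 patients.

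Footnote 1 of 8.2 permits omission, and 13.1 lets the investigator withdraw a patient. Neither directs what to do in this band, whereas the row above 500 msec does direct omission. Going to 25 mg once daily can be inferred from the non-hematologic row, but it departs from this row's explicit target.

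The phrase about one dose level reads awkwardly and may be a remnant of editing or PDF conversion. The point does not depend on it, because the fixed target fails at the lower doses with or without those words.

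Four stronger readings are tempting, and the documents do not support them:

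- **That a repeat ECG still in the band has no instruction after the row's own first use.** It has one: the 25 mg bid dose runs to the end of the cycle, and return depends on QTc falling to 470 msec or less.
- **That the 28-day interval is continuous unmonitored dosing.** On the usual schedule half of it is off drug and an ECG precedes the next course.
- **That the row orders an increase at 25 mg once daily.** The verb is to decrease; the instruction simply cannot be carried out.
- **That resuming the initial dose contradicts 9.4.** With one dose in 8.1, the initial dose is naturally 50 mg bid, and the 9.4 cut can be applied on top.

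**Conclusion.** The defect is real but minor, and confined to patients already below 50 mg bid for a reason other than QTc. For them the stated dose step gives 0% reduction with no triggered 7-day ECG at 25 mg bid, and cannot be carried out at 25 mg once daily. The stakes are patient safety and consistent dosing. A reader might infer an effect on the efficacy result, but the primary endpoint and the decision rule do not depend on this row.

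The documents give no rates for dose reductions or for QTc events, so no patient count is estimated; that few are likely to be affected is a judgement from the narrow routes and the size of the trial. The conclusion takes 8.1 as read, with one level. If lower levels were lost in conversion, the fixed target would still give no reduction at 25 mg bid and would still exceed the dose at 25 mg once daily.

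**What to change.** In 8.1, list the doses the plan already uses: level 0 = 50 mg bid, level −1 = 25 mg bid, level −2 = 25 mg once daily. The sponsor should confirm them.

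Replace the dose instruction in the row for QTc above 470 and up to 500 msec with:

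> At 50 mg bid, reduce to 25 mg bid until the cycle ends. If already at 25 mg bid for a reason other than QTc, reduce to 25 mg once daily until the cycle ends. If at 25 mg once daily, omit midostaurin until the cycle ends. Obtain an ECG 7 days after any event in this band, whether or not the dose changes.

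State that a patient at 25 mg bid because of this row stays there until QTc is 470 msec or less. Keep resumption at the initial dose, specified as 50 mg bid, so that a patient with QTc events in consecutive cycles can still return to it. Add only that resumption is subject to the 9.4 reduction while a strong CYP3A4 inhibitor continues, and to any reduction still in force for other toxicity. The 450-470 msec row and the omission above 500 msec need no change.

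The cost is a table amendment with no new patients. The downside is an occasional extra reduction, omission or ECG in patients already on a reduced dose; the ECGs are research-funded under 19.2.

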7.14 **Stem Cell Transplantation (SCT):** Allogeneic stem cell transplantation for intermediate and high risk patients (based on treating MD assessment) will be allowed at any time if a suitable donor is found and patient performance status allows. Decitabine and Midostaurin will be discontinued and the patient will go to event monitoring per section 18.0

7.15 If either drug is discontinued during treatment, the patient will go to event monitoring per section 18.0

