8.0 Dosage Modification Based on Adverse Events

ALERT: *ADR reporting may be required for some adverse events (See Section 10)*

- Omit = The current dose(s) for the specified drug(s) during a cycle is skipped. The patient does not make up the omitted dose(s) at a later time
- Hold/Delay = The current dose(s) of all drugs during a cycle is delayed. The patient does make up the delayed dose(s) when the patient meets the protocol criteria to restart drugs.
- Discontinue = The specified drug(s) are totally stopped.

Note: If either drug is discontinued during treatment, the patient will go to event monitoring per section 18.0

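### Section 8.2 gives two incompatible instructions for related Grade 4 vomiting, diarrhea and pneumonitis and does not say which prevails

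*Combined protocol and SAP*

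**What the plan says.** The Section 8.2 table governs midostaurin after adverse events at least possibly related to treatment. Three of its rows are headed Grade 3 or 4 and give these actions:

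- Nausea or vomiting: if the event "persists despite use of standard anti-emetic therapy, omit midostaurin until recovery to Grade 2 (or at least 3 days) then restart". Discontinuation comes later and is conditional: "If this is felt to be related to study drug and the re-challenge results in a subsequent Grade 3 or 4 toxicity", the patient comes off treatment.
- Diarrhea: if it persists despite "standard anti-diarrheal therapy(see section 9.4), omit midostaurin until recovery to Grade 2 (or at least 3 days) then restart".
- Pneumonitis: "Omit midostaurin until recovery to ≤ Grade 1 and then resume dosing".

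The last row, for other non-hematological events, says "Discontinue midostaurin for non-hematologic grade 4 toxicity (including grade 4 vomiting, diarrhea, and pneumonitis".

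Section 8.0 defines omitting as skipping the current doses without making them up, and then says "Discontinue = The specified drug(s) are totally stopped". Section 7.15 adds: "If either drug is discontinued during treatment, the patient will go to event monitoring per section 18.0". Section 13.1 lists discontinuation of either drug among the criteria for moving to event monitoring.

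**The concern.** A physician facing a related Grade 4 event of one of these three kinds finds a row telling them to interrupt and then resume, and another telling them to stop for good. Each course has support in the text, and nothing states which governs. One patient could be re-exposed after a Grade 4 toxicity while another with the same event leaves protocol therapy, and a monitor could not say with confidence which was the deviation. This is a safety instruction, so the stake is patient protection and consistent handling. No effect on evaluability, the significance level, power or the 5-of-24 decision rule is claimed.

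**Working it through.** The check is a comparison of text; the protocol gives no figure to reproduce. For a related Grade 4 event:

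| Event | Event's own row | Other non-hematological row | Conflict |
|---|---|---|---|
| Pneumonitis | Omit, then resume at Grade 1 or lower | Discontinue | Always |
| Vomiting | Omit, then restart, if persistent despite anti-emetics | Discontinue | When persistent |
| Diarrhea | Omit, then restart, if persistent despite anti-diarrheals | Discontinue | When persistent |

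1. **Are the actions really different?** Yes. Under Section 8.0 an omitted drug can continue and a discontinued drug cannot. Sections 7.15 and 13.1 attach a further consequence to discontinuation only.

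2. **Does the persistence condition remove the conflict?** Only in part. Grade 4 vomiting or diarrhea that settles with standard therapy meets the discontinue rule alone. The persistent case meets both rules, so the worse course is the one that also qualifies for restart. Pneumonitis carries no such condition.

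3. **Does a general rule rank the rows?** The sentence under the table, "All dose modifications should be based on the worst preceding toxicity", selects the toxicity to act on. A Grade 4 event still falls under both rows. The exits in Section 13.1 let the investigator withdraw a patient for an adverse event, but do not say whether restarting is permitted.

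4. **Does the table's layout settle it?** The signals point both ways. The parenthetical names the three events at Grade 4, which favors discontinuation. But the row is labelled as covering other events, and these three have rows of their own that expressly include Grade 4.

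5. **How often could it arise?** The only rates available are those for study 2104E1 in Section 1.2, which pool 50 mg and 100 mg twice daily and count events regardless of relationship:
   - Grade 3 or 4 diarrhea: 0.05 × 95 = 4.75, about 5 patients.
   - Grade 3 vomiting: 0.01 × 95 = 0.95, about 1 patient. No Grade 4 vomiting figure is given.
   - Pneumonitis does not appear in the midostaurin toxicity list in Section 15.17.

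   The protocol gives no rate for related Grade 4 events alone, so no count is projected for the 26 patients planned here.

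**The case against.** The strongest reply is that the intended rule can be recovered. The parenthetical names both the event and the exact grade, which is more specific than a heading covering Grades 3 and 4. On that reading the specific rows govern Grade 3 and the last row governs Grade 4. The re-challenge wording in the vomiting row fits a first event of Grade 3 followed by a second of Grade 3 or 4, so by itself it does not show that rechallenge after a first Grade 4 event was meant. The overlap is also narrow, the trial is small, and there are safeguards: treatment starts at one campus under a hematologist (Section 6.9a), the investigator may withdraw a patient, related Grade 4 non-hematologic events count toward accrual suspension (Section 16.42), and the DSMB reviews safety data at least twice a year.

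Much of this stands. Discontinuation is the likelier intent, the events should be few, and the safeguards limit the harm. It does not remove the inconsistency. If every Grade 4 event meant discontinuation, the mention of Grade 4 in the three headings would authorize nothing, yet it is there with a restart or resume instruction attached. Likely intent is not a stated precedence rule. The safeguards act through investigator discretion or on totals across patients; none tells the physician which row applies to the patient at hand.

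**Conclusion.** The concern holds. For related Grade 4 events, all three named toxicities have a row of their own whose action differs from that of the last row: one conflicts unconditionally (pneumonitis), and two conflict when the event persists despite standard therapy (vomiting and diarrhea). This rests on the protocol's wording and its own definitions, with no assumed rates. The number of patients affected is probably small but cannot be estimated from the documents. The point should be fixed because it is an operative safety instruction and the correction is simple; it does not threaten the trial's statistical conclusions.

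**What to change.** Limit the nausea or vomiting, diarrhea and pneumonitis rows to Grade 3, so that Grade 4 means discontinue, as the parenthetical suggests. Any Grade 4 nausea would then fall under the general Grade 4 rule. If rechallenge after Grade 4 is intended, delete the parenthetical and exempt these events from that rule explicitly.

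The same amendment should say whether the Grade 3 or 4 bilirubin, AST or ALT row, which also allows rechallenge, is an exception to the general Grade 4 rule. Two clerical points can be corrected with it; neither is needed for the finding:

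- The diarrhea row refers to Section 9.4, which deals with antifungals.
- The last row has midostaurin held for Grade 3 events. Section 8.0 defines a hold as delaying all drugs, and the footnotes in Sections 7.1 and 8.2 do not allow midostaurin to be held while decitabine is given. The term should be omitted.

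The cost is a text amendment, with no added visits, procedures or patients. The discontinue option has one real downside: a few patients with related Grade 4 events would leave protocol therapy and lose the chance of rechallenge.

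### Section 8.2 tells the investigator both to restart and to discontinue midostaurin after Grade 4 vomiting, diarrhea or pneumonitis

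*Combined protocol and SAP*

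**What the plan says.** Section 8.2 applies to adverse events at least possibly related to treatment, graded by CTCAE version 4.0.

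- **Nausea or vomiting, Grade 3 or 4.** If the event persists despite anti-emetics, "omit midostaurin until recovery to Grade 2 (or at least 3 days) then restart". Treatment is discontinued only if a re-challenge brings another Grade 3 or 4 event felt to be related.
- **Diarrhea, Grade 3 or 4.** If it persists despite "standard anti-diarrheal therapy(see section 9.4), omit midostaurin until recovery to Grade 2 (or at least 3 days) then restart". This row has no discontinuation step.
- **Pneumonitis.** The row is headed "Grade 3 or 4 Pneumonitis". Midostaurin is omitted until recovery to at most "Grade 1 and then resume dosing". There is no persistence condition and no discontinuation step.
- **Liver.** The row is headed "Grade 3 or 4 increased Bilirubin, AST, or ALT". Once other causes have been managed and the dysfunction persists, "Omit midostaurin until recovery to Grade 2 then restart". If the event is felt to be related and "re-challenge results in a subsequent Grade 3 or 4 elevation, then patient should be discontinued from treatment".
- **Other non-hematological events (last row).** "Discontinue midostaurin for non-hematologic grade 4 toxicity (including grade 4 vomiting, diarrhea, and pneumonitis". For other Grade 3 events, midostaurin waits for recovery to Grade 2 or lower.

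Section 8.0 defines omission as skipping a dose that is not made up, and discontinuation as stopping the drug altogether. Sections 7.15 and 8.0 send a patient who discontinues either drug to event monitoring.

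**The concern.** A patient with Grade 4 pneumonitis, or with persisting Grade 4 vomiting or diarrhea, meets two rules in the same table. One allows midostaurin again after recovery. The other ends it for good and, through Section 8.0, ends protocol treatment with decitabine as well. An investigator who finds the event's own row and stops there may re-expose a patient whom the last row says must stop. Two patients with the same event can be handled in opposite ways, and each can be defended from the text.

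Two lesser uncertainties sit in the same table. Grade 4 bilirubin, AST or ALT has its own re-challenge row but also falls within the general wording of the last row. And the three-day clause in the two gastrointestinal rows can be read as allowing restart while the event is still Grade 3.

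**Working it through.** The main point is a comparison of texts; the plan gives no figure for it.

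**1. The rows side by side, at Grade 4**

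| Event | Own row in 8.2 | Last row of 8.2 | Result |
|---|---|---|---|
| Vomiting (persisting) | Omit, restart; stop only after failed re-challenge | Discontinue; named | Contradiction |
| Diarrhea (persisting) | Omit, restart; no stop step | Discontinue; named | Contradiction |
| Pneumonitis | Omit to Grade 1 or lower, resume; no stop step | Discontinue; named | Contradiction |
| Bilirubin, AST, ALT | Omit to Grade 2, restart; stop after failed re-challenge | Not named; within general wording | Unclear |

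**2. Does other text settle it?** The note under the table bases modifications on the worst preceding toxicity. That picks the grade, not the row. The label of the last row suggests leftover events only, yet the row names three events that have rows of their own, so the label does not reliably exclude anything. No sentence in Sections 7, 8 or 13 says which row prevails.

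**3. Size for one patient, Grade 4 event in cycle 1 that recovers**

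- Maximum 18 cycles (7.12). Own row followed: up to 18 − 1 = 17 further cycles. With no response by the end of cycle 8 (7.11): up to 8 − 1 = 7. Last row followed: 0.
- Scheduled on-treatment marrows on day 1 of cycles 3, 5 and 9 (7.11): up to 3 against 0. The end-of-treatment marrow remains under both.

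The 17 is a ceiling. It needs a cycle 1 event, recovery, sustained response and completion of all 18 cycles.

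**4. The three-day clause.** This uses the diarrhea row, which has no re-challenge stop. Midostaurin twice daily on days 8 to 21 gives 14 × 2 = 28 doses. Assume omission starts with the first dose on day 10 and Grade 3 lasts through day 12, 16 or 21; these days are assumptions.

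- Recovery required: (12 − 10 + 1) × 2 = 6; (16 − 10 + 1) × 2 = 14; (21 − 10 + 1) × 2 = 24 doses omitted.
- Three days as an alternative to recovery: the table heading applies its rows afresh at each next dose, so a patient restarted at Grade 3 meets the row again. The pattern is omit 6, take 1, repeat. Of 6 dose times, 6 are omitted; of 14, 6 + 6 = 12; of 24, 6 + 6 + 6 + 3 = 21.
- Difference: 0, 2 or 3 doses taken while still at Grade 3.

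**5. Design figures.** With 5 or more successes required among 24, the exact binomial probability is 0.0851 at a true rate of 0.10 and 0.8889 at 0.30. These match the 0.09 and 0.89 in Section 16.24. Nothing in Section 8.2 enters that calculation.

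**The case against.** The best defence is that the last row names vomiting, diarrhea and pneumonitis precisely because they have rows elsewhere, so it must override those rows at Grade 4. As a reading of intent this is persuasive, and it stands. It does not repair the headings, which still state that omission and restart apply at Grade 4.

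The overlap is also narrower than the headings suggest. Grade 4 vomiting or diarrhea that does not persist despite standard therapy meets only the last row, so there is no conflict. That stands too, but a persisting event meets both rules and the pneumonitis row has no such condition.

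A reader might infer that the liver row is contradicted just as plainly. The documents do not support that: liver events are not among the named examples, the last row is labelled as covering other events, and the liver row has a complete re-challenge rule of its own. What remains is an uncertainty, since the named examples are not exhaustive.

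A reader might also infer that, under the literal three-day clause, omitting 6 doses is enough however long Grade 3 lasts, which would make the dose difference large. The table heading does not support that, because the row applies again at the next dose. The Grade 2 nausea or vomiting row is purely time-based, so a time-based intent cannot be ruled out. The Grade 3 liver, pneumonitis and other non-hematological rules, however, all require recovery.

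There are backstops. Investigators may withdraw a patient (13.1), related Grade 4 or higher non-hematologic events, apart from the listed exclusions, count toward accrual suspension whichever row is followed (16.42), and treatment starts at one centre under a hematologist (6.9a). They limit the harm without correcting the instruction.

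**Conclusion.** Section 8.2 is internally inconsistent, and wrong as written, for Grade 4 vomiting, diarrhea and pneumonitis. It should be corrected for patient safety and uniform handling. Confidence is high, because the point rests on wording alone.

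The consequence for one patient is re-exposure or permanent discontinuation: at most 17 further cycles against 0, under the assumptions in the working. The number of patients affected cannot be estimated. Section 1.2 reports Grade 3 or 4 diarrhea in 5% and Grade 3 or 4 AST/ALT abnormalities in 13% of a 95-patient single-agent study, so such events are plausible, but that population and regimen differ from this trial's.

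The liver question and the three-day clause are secondary. The latter amounts to 0 to 3 doses over the assumed durations.

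A reader might infer that the primary result is put at risk, since success is CR or CRi during therapy. The documents give no event frequency from which to show that, and alpha, power and the decision rule do not depend on these rows.

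**What to change.** In Section 8.2:

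1. Limit the nausea or vomiting, diarrhea and pneumonitis rows to Grade 3, and refer Grade 4 to the discontinuation rule in the last row.
2. Add one sentence saying which rule governs Grade 4 bilirubin, AST or ALT. If re-challenge is wanted, list liver events as an explicit exception in the last row.
3. In the two gastrointestinal rows, write: omit for at least 3 days and until recovery to Grade 2 or lower, then restart. The present text does not settle the meaning; this version is recommended because it matches the recovery requirement for other Grade 3 toxicities.

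The cost is a wording amendment with no added procedures. The downside is that Grade 4 cases leave protocol treatment, and slow recoverers may miss a few more doses (0, 2 or 3 in the assumed cases).
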